9.12 Prohibited Medication

The following medications are excluded while the patient is receiving study treatment:

- Any other HDAC inhibitor, including valproic acid
- DNA methyltransferase inhibitors
- Any additional investigational or commercial anticancer agents, such as chemotherapy, immunotherapy, targeted therapy, biological response modifiers, or endocrine therapy, will not be allowed, even if utilized as treatment of non-cancer indications.
- Prophylactic use of hematopoietic colony stimulating factors are not allowed during the Phase 1b, but can be used per investigator discretion during other parts of the study.
- Radiation therapy

Note: Radiation therapy to a symptomatic solitary lesion or to the brain may be considered on an exceptional case-by-case basis after consultation with the Medical Monitor. The radiation field cannot encompass a target lesion. Radiation to a target lesion is considered progressive disease and the subject should be removed from study treatment. The patient must have clear measurable disease outside the radiated field. Administration of palliative radiation therapy will be considered clinical progression.

- Traditional herbal medicines; these therapies are not fully studied and their use may result in unanticipated drug-drug interactions that may cause or confound the assessment of toxicity
- RANKL inhibitor (denosumab): patients who are receiving denosumab prior to randomization must be willing and eligible to receive a bisphosphonate instead while on study
- Immunomodulatory agents, including but not limited to interferons or IL-2, during the entire study; these agents could potentially increase the risk for autoimmune conditions when received in combination with atezolizumab
- Immunosuppressive medications, including but not limited to cyclophosphamide, azathioprine, methotrexate, and thalidomide; these agents could potentially alter the activity and the safety of atezolizumab
- Use of steroids to premedicate patients for whom CT scans with contrast are contraindicated (i.e., patients with contrast allergy or impaired renal clearance); in such patients, MRIs of the chest, abdomen, and pelvis with a non-contrast CT scan of the chest must be performed
- Any live, attenuated vaccine (e.g., FluMist®) while the patient is receiving atezolizumab and for a period of 90 days after the discontinuation of atezolizumab

Influenza vaccinations (inactivated forms only) should be given during influenza season only (approximately October to March in the Northern hemisphere and April to September in the Southern Hemisphere).

Systemic corticosteroids and anti-TNF- α agents may attenuate potential beneficial immunologic effects of treatment with atezolizumab. If feasible, alternatives to these agents should be considered. Systemic corticosteroids may be administered at the discretion of the treating physician in consultation with the Medical Monitor at doses no greater than 10 mg prednisone or for no longer than 7 consecutive days if at higher doses, to treat acute conditions other than immune-mediated toxicity related to study drug. The use of physiologic doses of corticosteroids for prolonged periods may be approved in consultation with the Medical Monitor. Inhaled steroids are allowed for management of asthma or other chronic disorders, as prescribed.

Patients should not receive other immunomodulatory agents for 10 weeks after the last dose of atezolizumab.

Patients who, in the assessment by the Investigator, require the use of any of the aforementioned treatments for clinical management should be removed from the study, unless as otherwise noted. Patients may receive other medications that the Investigator deems to be medically necessary.

The exclusion criteria ([Section 7.2](#)) describe other medications that are prohibited in this study.

9.13 Medications to be Avoided During the Study

Concomitant use of the drugs below with entinostat should be avoided during the study:

- Sensitive substrates of CYP enzymes listed in Appendix 2
- Drugs that are known to inhibit or induce P-gp (see Appendix 2)

Should the use of these medications be required, the Medical Monitor must be consulted for guidance.

9.14 Management for Atezolizumab-Specific Adverse Events

Toxicities associated with, or possibly associated with atezolizumab treatment, should be managed according to standard medical practice. Additional tests, such as autoimmune serology or biopsies, should be used to determine a possible immunogenic etiology.

Although most immune-mediated adverse events observed with immunomodulatory agents have been mild and self-limiting, such events should be recognized early and treated promptly

to avoid potential major complications. Discontinuation of atezolizumab may not have an immediate therapeutic effect and, in severe cases, immune-mediated toxicities may require acute management with topical corticosteroids, systemic corticosteroids, mycophenolate, or TNF- α inhibitors.

The investigator should consider the benefit-risk balance for a given patient prior to further administration of atezolizumab. Atezolizumab should be permanently discontinued in patients with life-threatening immune-mediated adverse events.

For the management of other adverse events associated with the atezolizumab not provided below, refer to the Atezolizumab IB.

9.14.1 Pulmonary Events

Dyspnea, cough, fatigue, hypoxia, pneumonitis, and pulmonary infiltrates have been associated with the administration of atezolizumab.. Patients will be assessed for pulmonary signs and symptoms throughout the study and will also have CT scans of the chest performed at every tumor assessment.

All pulmonary events should be evaluated thoroughly for other commonly reported etiologies such as pneumonia/infection, lymphangitic carcinomatosis, pulmonary embolism, heart failure, chronic obstructive pulmonary disease, or pulmonary hypertension. by the following means:

Measurement of oxygen saturation (i.e., arterial blood gas)

Bronchoscopy with bronchoalveolar lavage and biopsy

Pulmonary function tests (diffusion capacity of the lung for carbon monoxide [DL_{CO}])

Pulmonary function testing with a pulmonary embolism protocol

Table 9-3 Management Guidelines for Pulmonary Events, Including Pneumonitis

Severity	Management
Grade 1	
Continue atezolizumab with close monitoringRe-evaluate on serial imagingConsider pulmonary consultation
Grade 2	
Withhold atezolizumab for up to 12 weeks after event onset.^aPulmonary and infectious disease specialists consultation and consider bronchoscopy or bronchoscopic alveolar lavage (BAL)Start treatment with 1–2 mg/kg/day oral prednisone or equivalentWhen improves to Grade 0 or Grade 1, then taper steroids over ≥ 1 month. Atezolizumab may be resumed if the event improves to Grade 0 or Grade 1^bIf event does not resolve to Grade 1 or better while withholding atezolizumab, permanently discontinue atezolizumab and contact Medical Monitor^cTreat as Grades 3–4 for recurrent events
Grades 3–4	
Permanently discontinue atezolizumab and contact Medical Monitor^cBronchoscopy/BAL is recommendedStart treatment with 1–2 mg/kg/day oral prednisone or equivalentTaper steroids over ≥ 1 month after symptoms improve to Grade 0 or Grade 1If not improving within 48 hours after initiating corticosteroids, consider adding an immunosuppressive agent

^a Atezolizumab may be withheld for a longer period of time (i.e., > 12 weeks after event onset) to allow for corticosteroids (if started) to be reduced to ≤ 10 mg/day oral prednisone or equivalent. The acceptable length of the extended period of time must be agreed upon by the investigator and the Medical Monitor.

^b If corticosteroids have been started, they must be tapered over ≥ 1 month to ≤ 10 mg/day oral prednisone or equivalent before atezolizumab can be resumed.

^c Resumption of atezolizumab may be considered in patients who are deriving benefit and have fully recovered from the immune-related event. Patients can be re-challenged with atezolizumab only after approval has been documented by both the investigator (or an appropriate delegate) and the Medical Monitor.

9.14.2 Hepatic Events

Immune-mediated hepatitis has been associated with the administration of atezolizumab.

Eligible patients must have adequate liver function, as manifested by measurements of total bilirubin and hepatic transaminases, and liver function will be monitored throughout study treatment.

While in this study, patients who present with right upper-quadrant abdominal pain and/or unexplained nausea or vomiting should have liver function tests (LFTs) performed immediately and reviewed before administration of the next dose of study drug.

If LFTs increase, concurrent medications, viral hepatitis, and toxic or neoplastic etiologies should be considered and addressed, as appropriate. Imaging of the liver, gall bladder, and biliary tree should be performed to rule out neoplastic or other causes for increased LFTs. Anti-nuclear antibody, perinuclear anti-neutrophil cytoplasmic antibody, anti-liver kidney microsomal antibodies, and anti-smooth muscle antibody tests should be performed if an autoimmune etiology is considered.

Table 9-4 Management Guidelines for Hepatic Events

Severity	Management
Grade 1	
Continue atezolizumabContinue LFT monitoring until values resolve to within normal limits
Grade 2	
All Events:
 
Monitor LFTs at least twice a week until return to baseline values 
Events of > 5 days' duration:
 
Withhold atezolizumab for up to 12 weeks after event onset.^aInitiate treatment with 1–2 mg/kg/day oral prednisone or equivalent.If event resolves to Grade 0 or Grade 1, resume atezolizumab^bIf corticosteroids have been started, they must be tapered over ≥1 month to ≤10 mg/day oral prednisone or equivalent before atezolizumab can be resumed.If event does not resolve to Grade 0 or Grade 1 while withholding atezolizumab, permanently discontinue atezolizumab and contact Medical Monitor^cIf persists >5–7 days: withhold therapy and start 60 mg prednisone or equivalent per day; when LFTs are ≤Grade 1, taper steroids over ≥1 month, resume therapy if the event improves to Grade 0 or Grade 1 within 12 weeks and systemic steroid dose is ≤10mg oral prednisone equivalent per day.
Grades 3–4	
Permanently discontinue atezolizumab and contact Medical Monitor. ^cConsider gastrointestinal (GI) specialist consult and liver biopsy to establish etiology of hepatic injuryStart 1-2 mg/kg/day oral prednisone or equivalentIf event does not improve within 48 hours after initiation of corticosteroids, consider adding an immunosuppressive agentTaper steroids over ≥1 month, when symptoms improve to Grade 0 or Grade 1

^a Atezolizumab may be withheld for a longer period of time (i.e., > 12 weeks after event onset) to allow for corticosteroids (if started) to be reduced to ≤10 mg/day oral prednisone or equivalent. The acceptable length of the extended period of time must be agreed upon by the investigator and the Medical Monitor.

^b If corticosteroids have been started, they must be tapered over ≥1 month to ≤10 mg/day oral prednisone or equivalent before atezolizumab can be resumed.

^c Resumption of atezolizumab may be considered in patients who are deriving benefit and have fully recovered from the immune-related event. Patients can be rechallenged with atezolizumab only after approval has been documented by both the investigator (or an appropriate delegate) and the Medical Monitor.

9.14.3 Gastrointestinal Events

Immune-mediated colitis has been associated with the administration of atezolizumab.

All events of diarrhea or colitis should be thoroughly evaluated for other more common etiologies. If the event is of significant duration or magnitude or is associated with signs of systemic inflammation or acute phase reactants (e.g., increased C-reactive protein, platelet count, or bandemia), perform sigmoidoscopy (or colonoscopy, if appropriate) with colonic biopsy with three to five specimens for standard paraffin block to check for inflammation and lymphocytic infiltrates for confirmation of the diagnosis of colitis.

Perform laboratory tests to rule out alternate etiology (i.e., WBCs and stool calprotectin).

Table 9-5 Management Guidelines for Gastrointestinal Events (Diarrhea/Colitis)

Severity	Management
Grade 1	
Continue atezolizumabSymptomatic treatmentEndoscopy is recommended if symptoms persist for greater than 7 daysClose monitoring
Grade 2	
Withhold atezolizumab for up to 12 weeks after event onset ^aSymptomatic treatmentGI consultation recommendedIf persists >5 days or recurs start oral prednisone 1-2 mg/kg/day or equivalentTaper steroids over \geq1 month when symptoms improve to Grade 0 or Grade 1may be resumed if the event improves to Grade 0 or Grade 1^bIf event does not resolve to Grade 0 or Grade 1 while withholding atezolizumab, permanently discontinue atezolizumab and contact Medical Monitor ^c
Grade 3	
Withhold atezolizumab for up to 12 weeks after event onset ^aGI referral and confirmation biopsyStart treatment with IV steroids 1-2 mg/kg/day methylprednisolone or equivalent and convert to 1-2 mg/kg/day oral prednisone or equivalent after improvementWhen improves to Grade 0 or Grade 1, then taper steroids over \geq1 month.may be resumed if event improves to Grade 0 or Grade 1^bIf event does not resolve to Grade 1 or better while withholding atezolizumab, permanently discontinue atezolizumab and contact Medical Monitor ^c
Grade 4	
Permanently discontinue atezolizumab and contact Medical Monitor ^cGI referral and confirmation biopsyStart treatment with IV steroids 1-2 mg/kg/day methylprednisolone or equivalent and convert to 1-2 mg/kg/day oral prednisone or equivalent after improvementWhen patient's diarrhea or colitis improves to Grade 0 or Grade 1, then taper steroids over \geq1 monthIf not improving within 48 hours of initiating corticosteroids, consider adding an immunosuppressive agent

IV=intravenous

^a Atezolizumab may be withheld for a longer period of time (i.e., >12 weeks after event onset) to allow for corticosteroids (if initiated) to be reduced to \leq 10 mg/day oral prednisone or equivalent. The acceptable length of the extended period of time must be agreed upon by the investigator and the Medical Monitor.

^b If corticosteroids have been initiated, they must be tapered over \geq 1 month to \leq 10 mg/day oral prednisone or equivalent before atezolizumab can be resumed. Resumption of atezolizumab may be considered in patients who are deriving benefit and have fully recovered from the immune-related event. Patients can be rechallenged with atezolizumab only after approval has been documented by both the investigator (or an appropriate delegate) and the Medical Monitor

9.14.4 .Endocrine Events

Thyroid disorders, adrenal insufficiency, diabetes mellitus and pituitary disorders have been associated with the administration of atezolizumab.

Patients with unexplained symptoms such as headache, fatigue, myalgias, impotence, mental status changes, or constipation should be investigated for the presence of thyroid, pituitary, or adrenal endocrinopathies. An endocrinologist should be consulted if an endocrinopathy is suspected. Thyroid-stimulating hormone (TSH) and free triiodothyronine (T3) and thyroxine (T4) levels should be obtained to determine whether thyroid abnormalities are present. Pituitary hormone levels and function tests (e.g. TSH, growth hormone, luteinizing hormone, follicle-stimulating hormone, testosterone, prolactin, adrenocorticotrophic hormone [ACTH] levels and ACTH stimulation test) and magnetic resonance imaging (MRI) of the brain (with detailed pituitary sections) may help to differentiate primary adrenal insufficiency from primary pituitary insufficiency.

Table 9-6 Management Guidelines for Endocrine Events

Severity/Event	Management
Asymptomatic hypothyroidism	
 Continue atezolizumab Start thyroid replacement hormone Monitor TSH weekly
Symptomatic hypothyroidism	
 Withhold atezolizumab. Start thyroid replacement hormone Monitor TSH weekly Consider referral to an endocrinologist. Restart atezolizumab when symptoms are controlled and thyroid function is improving
Asymptomatic hyperthyroidism	
If serum TSH ≥ 0.1 mU/L and < 0.5 mU/L:
 
 Continue atezolizumab. Monitor TSH every 4 weeks 
TSH < 0.1 mU/L:
 
Follow guidelines for symptomatic hyperthyroidism

Symptomatic hyperthyroidism	
 Withhold atezolizumab Initiate treatment with anti-thyroid drug such as methimazole or carbimazole as needed Consider referral to an endocrinologist Restart atezolizumab when symptoms are controlled by thyroid replacement and thyroid function is improving Permanently discontinue atezolizumab and contact Medical Monitor for life-threatening immune-related hyperthyroidism ^c
Symptomatic adrenal insufficiency, Grade 2–4	
 Withhold atezolizumab for up to 12 weeks after event onset ^a Refer patient to endocrinologist Perform appropriate imaging Initiate treatment with 1–2 mg/kg/day IV methylprednisolone or equivalent and convert to 1–2 mg/kg/day oral prednisone or equivalent upon improvement If event resolves to Grade 0 or Grade 1 and patient is stable on replacement therapy, resume atezolizumab ^b If event does not resolve to Grade 0 or Grade 1 or patient is not stable on replacement therapy while withholding atezolizumab, permanently discontinue atezolizumab and contact Medical Monitor ^c
Hyperglycemia Grade 1 or 2	
 Continue atezolizumab Start treatment with insulin if needed Monitor for glucose control

Table 9-6 Management Guidelines for Endocrine Events

Hyperglycemia, Grade 3 or 4	
 Withhold atezolizumab Start treatment with insulin Monitor for glucose control Resume atezolizumab when symptoms resolve and glucose levels are stable
Hypophysitis (pan-hypopituitarism), Grade 2-3	
 Withhold atezolizumab for up to 12 weeks after event onset ^a Refer patient to endocrinologist Perform brain MRI (pituitary protocol) Start treatment with 1–2 mg/kg/day IV methylprednisolone or equivalent and convert to 1–2 mg/kg/day oral prednisone or equivalent upon improvement ^a Initiate hormone replacement therapy if clinically indicated If event resolves to Grade 0 or Grade 1, resume atezolizumab ^b If event does not resolve to Grade 0 or Grade 1 while withholding atezolizumab, permanently discontinue atezolizumab and contact Medical Monitor ^c For recurrent hypophysitis, treat as a Grade 4 event
Hypophysitis (pan-hypopituitarism), Grade 4	
 Permanently discontinue atezolizumab and contact Medical Monitor ^c Refer patient to endocrinologist. Perform brain MRI (pituitary protocol) Start treatment with 1–2 mg/kg/day IV methylprednisolone or equivalent and convert to 1–2 mg/kg/day oral prednisone or equivalent upon improvement ^a Initiate hormone replacement therapy if clinically indicated

IV = intravenous; TSH = thyroid stimulating hormone; MRI = magnetic resonance imaging;

^a Atezolizumab may be withheld for a longer period of time (i.e., > 12 weeks after event onset) to allow for corticosteroids (if initiated) to be reduced to ≤ 10 mg/day oral prednisone or equivalent. The acceptable length of the extended period of time must be agreed upon by the investigator and the Medical Monitor.

^b If corticosteroids have been initiated, they must be tapered over ≥ 1 month to ≤ 10 mg/day oral prednisone or equivalent before atezolizumab can be resumed.

^c Resumption of atezolizumab may be considered in patients who are deriving benefit and have fully recovered from the immune-related event. Patients can be rechallenged with atezolizumab only after approval has been documented by both the investigator (or an appropriate delegate) and the Medical Monitor.

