9.10 Dose Interruptions and Modifications

Although entinostat and atezolizumab have distinct toxicity profiles, they do share some AEs such as fatigue and nausea. There is also the possibility that 1 agent may potentiate the other and hence drug causality will not always be clear. In the event of uncertainty, dose reductions or delays will follow the most conservative approach (i.e., delays and/or dose reductions for both drugs) until resolution of the event, or the patient is taken off study. However, if the toxicity is clearly associated with only one of the study drugs, then the other study drug may be continued at the discretion of the study investigator in consultation with the Medical Monitor, until resolution of the event or the patient is taken off study.

Note: If a patient permanently discontinues either study drug (entinostat/placebo or atezolizumab), the patient will be taken off study treatment

No dose reductions will be performed for atezolizumab.

Guidance for entinostat delays and or dose reductions can be found in Protocol [Section 9.10.1](#) . All dose modifications should be based on the AE requiring the greatest modification and should be properly documented in source documents. Investigators may take a more conservative approach than the guidelines outlined in the protocol on the basis of clinical judgment that is in the best interest of the subject. Such instances should be reported to the Medical Monitor.

Expected AEs for each agent are summarized in [Section 12](#).

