9.10.2 Atezolizumab

There will be no dose reduction for atezolizumab in this study.

Patients may temporarily suspend study treatment for up to 84 days beyond the last dose if they experience adverse events that require atezolizumab to be withheld. If atezolizumab is withheld because of atezolizumab related adverse events for >84 days beyond the last dose, then the patient will be discontinued from study treatment and will be followed up for safety and efficacy per protocol.

If, in the judgment of the investigator, the patient is likely to derive clinical benefit from atezolizumab after a hold of >84 days, and entinostat has been administered per protocol during this time, study drug may be restarted only with the approval of the Medical Monitor.

As discussed in Protocol [Section 9.12](#), systemic corticosteroids should be used to treat immune mediated toxicities related to atezolizumab. If a patient must be tapered off steroids used to treat adverse events, atezolizumab may be held for additional time beyond 84 days from the last dose until steroids are discontinued or reduced to prednisone dose (or dose equivalent) \leq 10 mg/day. The acceptable length of interruption will depend on an agreement between the investigator and the Medical Monitor.

Dose interruptions for reason(s) other than toxicity, such as surgical procedures, may be allowed with Medical Monitor approval. The acceptable length of interruption will depend on agreement between the investigator and the Medical Monitor .

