10.2.6 Clinical Laboratory Tests

Blood samples for hematology and clinical chemistries are to be collected during screening, on D1, D8 and D15 of C1; on D1 and D15 of C2; on D1 of each subsequent treatment cycle; and at the EOT visit. If screening hematology and clinical chemistry tests are performed within 7 days of enrollment, they need not be repeated at C1D1 unless clinically indicated.

The following analytes are to be measured:

Hematology

White blood cell count (WBC) with differential	Hemoglobin
Red blood cell count (RBC)	Hematocrit
Platelet count	Coagulation studies, including PT or INR and aPTT (screening only)

Clinical Chemistries

ALT	AST
Alkaline phosphatase	Albumin
Total bilirubin	Blood urea nitrogen (BUN)
Calcium	Creatinine
Sodium	Potassium
Chloride	Bicarbonate
Glucose	Lactic dehydrogenase
Phosphorus	Total Protein
Uric acid	Magnesium and TSH (screening only, unless clinically indicated)

In addition to the scheduled assessments, clinical laboratory evaluations are to be repeated as necessary during treatment at a schedule determined by the Investigator, based on the patient's clinical status.

Laboratory abnormalities that are considered by the Investigator to be clinically significant for a particular patient are to be reported as AEs.

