12.4.3 Adverse Events of Special Interest with Atezolizumab

Selected non-serious and SAEs are also known as AESI, Adverse Events of Special Interest. As noted in [Section 9.6](#), DLTs will also be captured as AESI. AESI must be recorded as such in

the AE eCRF, completing the same fields as for Serious Adverse Events, and reported within 24 hours to the Sponsor. Such events must be documented through 90 days following cessation of treatment, or 30 days after the initiation of a new anticancer therapy, whichever is earlier.

Sponsor Contact information can be found in the Study Manual.

Toxicities associated or possibly associated with atezolizumab treatment should be managed according to standard medical practice. Additional tests, such as autoimmune serology or biopsies, should be used to determine a possible immunogenic etiology.

Although most immune-mediated adverse events observed with immunomodulatory agents have been mild and self-limiting, such events should be recognized early and treated promptly to avoid potential major complications. Discontinuation of atezolizumab may not have an immediate therapeutic effect and, in severe cases, immune-mediated toxicities may require acute management with topical corticosteroids, systemic corticosteroids, mycophenolate, or TNF- α inhibitors.

The investigator should consider the benefit-risk balance for a given patient prior to further administration of atezolizumab. Atezolizumab should be permanently discontinued in patients with life-threatening immune-mediated adverse events.

For the management of other adverse events associated with the atezolizumab not provided below, refer to the Atezolizumab IB. Patients should be assessed for possible AESIs prior to each dose of study medication. Laboratory results should be evaluated and patients should be asked for signs and symptoms suggestive of an immune-related event. Patients who develop an AESI thought to be immune-related should have additional testing to rule out other causes. If laboratory results or symptoms indicate a possible immune-related AESI, then additional testing should be performed to rule out other causes. If no other cause is found, then it is assumed to be immune-related.

The following conditions may be suggestive of an autoimmune disorder and are considered AESI for this study:

- Pneumonitis
- Colitis
- Endocrinopathies: Diabetes mellitus, Pancreatitis, Adrenal Insufficiency, Hyperthyroidism, and Hypophysitis
- Vasculitis

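### Table 9-6 makes atezolizumab restart after symptomatic hyperthyroidism depend on thyroid replacement, a treatment that row never starts

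*Protocol*

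**What the plan says.** Protocol Section 9.14.4, Table 9-6, gives management rules for endocrine events attributed to atezolizumab. For symptomatic hyperthyroidism the row withholds atezolizumab and continues: "Initiate treatment with anti-thyroid drug such as methimazole or carbimazole as needed". It suggests considering an endocrinology referral. The restart bullet is: "Restart atezolizumab when symptoms are controlled by thyroid replacement and thyroid function is improving". A last bullet sends life-threatening immune-related cases to permanent discontinuation; its footnote allows rechallenge after full recovery, with documented approval from the investigator and the Medical Monitor.

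Two neighbouring rows bear on this one. The symptomatic hypothyroidism row starts thyroid replacement hormone and has this restart bullet: "Restart atezolizumab when symptoms are controlled and thyroid function is improving". The asymptomatic hyperthyroidism row deals with patients whose TSH is below 0.1 mU/L by cross-reference: "Follow guidelines for symptomatic hyperthyroidism".

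The symptomatic hyperthyroidism row states no maximum hold. Section 9.10.2 sets the general limit, for drug that is being: "withheld because of atezolizumab related adverse events for >84 days beyond the last dose, then the patient will be discontinued from study treatment". Section 9.10 extends any permanent stop to both drugs: "If a patient permanently discontinues either study drug (entinostat/placebo or atezolizumab), the patient will be taken off study treatment".

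**The concern.** The restart bullet names a treatment that its own row does not prescribe and that works against the one it does. This is an operative rule for resuming study drug, so a site has to apply it. If the site follows the wording, it keeps withholding atezolizumab from a patient who is clinically ready while the 84-day limit runs. If it restarts on clinical judgement, it departs from the written condition.

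Hyperthyroidism is foreseen in this trial. Section 12.4.3 lists it among the adverse events of special interest: "Endocrinopathies: Diabetes mellitus, Pancreatitis, Adrenal Insufficiency, Hyperthyroidism, and Hypophysitis". That listing governs reporting and does not make the restart bullet more consequential. The stake is avoidable loss of study treatment, at worst of both drugs, in a small and unquantified group of patients.

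**Working it through.** No alpha, power or event count is involved. The check compares the thyroid rows of Table 9-6, followed by one piece of arithmetic on the hold limit.

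| Row | Atezolizumab | Treatment named | Restart condition |
|---|---|---|---|
| Asymptomatic hypothyroidism | Continue | Thyroid replacement | None needed |
| Symptomatic hypothyroidism | Withhold | Thyroid replacement | Symptoms controlled, thyroid function improving |
| Asymptomatic hyperthyroidism, TSH 0.1 to below 0.5 mU/L | Continue | None | None needed |
| Asymptomatic hyperthyroidism, TSH below 0.1 mU/L | As symptomatic row | As symptomatic row | As symptomatic row |
| Symptomatic hyperthyroidism | Withhold | Anti-thyroid drug, as needed | Symptoms controlled *by thyroid replacement*, thyroid function improving |

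Thyroid replacement is started only in the two hypothyroidism rows. The hypophysitis rows mention hormone replacement in general, where clinically indicated. Neither the Section 9.14.4 text nor the table footnotes give a reason to require replacement in a hyperthyroid patient. The two restart bullets differ only by the three extra words, and those words sit in the row where they do not fit.

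Applying the bullet literally to the patients who reach this row:

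- Controlled on methimazole or carbimazole, thyroid function improving: not met, because control did not come from replacement.
- Settled without any drug (the anti-thyroid drug is only as needed): not met, for the same reason.
- No symptoms, TSH below 0.1 mU/L: no symptoms for replacement to control, so the condition cannot sensibly be applied.
- Later became hypothyroid and was put on replacement: could be met, but the row neither describes this course nor limits the condition to it.

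The third group is likely to be small. Section 10.2.6 limits routine testing: "Magnesium and TSH (screening only, unless clinically indicated". A TSH below 0.1 mU/L would therefore come from a clinically indicated test, or from the repeat TSH monitoring that Table 9-6 itself sets once a thyroid abnormality is known.

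Hold limit. The inputs are the 21-day atezolizumab interval (Section 9.3.2) and the limit of more than 84 days beyond the last dose (Section 9.10.2).

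- 84 ÷ 21 = 4 dosing intervals, so infusions fall due on days 21, 42, 63 and 84 after the last dose.
- Day 84 is still within the limit. A patient restarting then has missed days 21, 42 and 63, which is 3 infusions.
- After day 84 the discontinuation rule applies and, under Section 9.10, entinostat/placebo stops too.

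**The case against.** The strongest reply is that harm needs an unlikely reading. An investigator would have to treat hyperthyroidism, see symptoms controlled and thyroid function improving, and still withhold because no replacement hormone was given. The table is headed as guidelines. Section 9.14 calls for standard medical practice and a benefit-risk judgement before further atezolizumab. The Section 9.14.4 text calls for an endocrinologist to be consulted when an endocrinopathy is suspected, although the row itself only suggests considering referral. Section 9.10.2 lets the Medical Monitor approve a restart after 84 days. Three missed infusions is arithmetic on that limit, not a predicted consequence of the phrase. Some patients in this row might also already be taking replacement, since Appendix 3 allows entry with autoimmune hypothyroidism on a stable dose.

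Most of this stands as a statement about frequency. A wrong prescription is unlikely and long holds caused by the phrase should be rare. None of it makes the condition correct. Patients already on replacement do not rescue it, because the row is not limited to them. The Medical Monitor route also has a condition: entinostat must have been given per protocol during the hold. That may fail if causality was uncertain and both drugs were held, as Section 9.10 directs in that case.

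**Conclusion.** The restart condition is wrong as written, and the documents contain nothing that corrects it. Confidence in the mismatch is high. The cause is not stated; a drafting slip is the natural reading, because removing the phrase makes the bullet identical to the one in the symptomatic hypothyroidism row.

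It applies to symptomatic hyperthyroidism that is not life-threatening and to asymptomatic patients with TSH below 0.1 mU/L. The most it could cost one patient is three infusions within the limit, then loss of both study drugs beyond it. That assumes a site follows the wording literally and no Medical Monitor approval is obtained. The number of patients affected cannot be estimated from the documents. The treatment instruction in the row is clear, and sample size, error rates and the primary analysis are unaffected. It should be corrected, but it is a local wording error in a safety-management rule.

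**What to change.** Delete *by thyroid replacement* from the restart bullet in the symptomatic hyperthyroidism row of Table 9-6, so that it reads "Restart atezolizumab when symptoms are controlled and thyroid function is improving", as in the symptomatic hypothyroidism row. That wording covers patients on an anti-thyroid drug, patients who needed no drug, and any who later need replacement. Substituting *by anti-thyroid treatment, if given* would also work.

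The cost is three words in one table cell at the next amendment, with no change to design, data collection or analysis.
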